## Translation to Human Therapies and the Choice of Drug and Dose

Safety Considerations and Potential Translation to Human Therapies. Fasudil is a specific ROCK inhibitor (63) approved for human use in Japan with an intravenous dose of 90 mg/day, for a period of 2 weeks to prevent cerebral vasospasm after aneurysmal subarachnoid hemorrhage (64). Experience with more chronic administration of fasudil in man is limited, and serious adverse events have been reported (65). Because of the paucity of experience and questionable safety in chronic use, and the expired worldwide patent on the drug, **there is currently no pathway for the approval of fasudil for chronic use in man.** The pharmaceutical industry is developing a number of potential ROCK1 or ROCK2 inhibitors for more specific targeting of peripheral and brain vasculature, respectively. While a ROCK2 inhibitor might enhance therapeutic effects on brain vessels including CAs, and minimize peripheral side effects (more likely mediated by ROCK1), such drug has not been used in humans and is now undergoing preclinical development (R44NS095420 grant with [name] as coPI). **A pharma pipeline for safer or more effective chronic ROCK inhibitors will require several years before potential Investigational New Drug (IND) and clinical trials in man.**

Therapeutic clinical trials with statins have already been advocated in CAs based on **statin inhibition of RhoA prenylation, a critical early step in RhoA/ROCK pathway activation** (37, 66, 67). A clinical database at University of Chicago includes 24 human subjects with known CAs enrolled in Institutional Review Board (IRB) approved NINDS funded biomarker studies, who are *receiving various statins for routine cardiovascular indications unrelated to their CA disease* (atorvastatin 10-80 mg; simvastatin 10-60 mg; lovastatin 80 mg). Among those patients followed for 247 lesion-years (T2-weighted lesions > 4 mm counted), there was only 1 documented SH (0.4 SH per 100 lesion-years). This rate is substantially lower than 173 bleeds during 1,604 lesion-years (T2-weighted lesions > 4 mm) of follow-up of statin naïve cases in the same database (10.7 SH per 100 lesion-years). While this data does not control for treatment assignment or dose effect, **it does not raise any concern about hemorrhage tendency among CA patients receiving statins** nor in comparison to bleed rates reported in the literature (18). Nor have there been any cases in the New Mexico trial (see below, and letter by [name]) nor any reported case in the published literature of CA hemorrhage after initiation of statin therapy (Search was performed on August 20th 2017 using MEDLINE portal for keywords “cerebral cavernous malformation”, “angioma” or “cavernoma” and “statin” or “atorvastatin” and “hemorrhage” or “bleeding”).

Statins have been widely used and well tolerated in neurosurgical patients, including (as with fasudil) for the treatment of vasospasm after subarachnoid hemorrhage (68). Statins have recently been reported to portend better outcome after intracerebral hemorrhage in man (69). In a meta-analysis of clinical trials of stroke prevention, including 83,205 patients, there was no evidence of increased hemorrhagic risk with long term statin use (70). Two clinical trials of stroke prevention (but not all others) did suggest a potentially increased hemorrhage risk with statin in secondary analyses (70). In one study, preconditioning and possibly the early withdrawal of statin were observed to worsen cerebral vasospasm after subarachnoid hemorrhage (71). Two recent reports associated statin use with cerebral aneurysm rupture (72) and with cerebral microbleeds in patients presenting with intracerebral hemorrhage (73), without establishing causation.

Considering all evidence class and level, current American Stroke Association guidelines on management and prevention of intracerebral hemorrhage include no restrictions on the use of statins in patients with hemorrhagic stroke (74). Altogether there is no hint of deleterious effects on statin-treated murine CA models (in fact statins resulted in *decreased* lesional hemorrhage), nor any suspected or reported harmful effects in humans with CA to date, **These cautious enthusiasm and concerns about other potentially harmful pleiotropic effects, create a veritable equipoise, motivating a need for specific and careful study of statins in hemorrhagic CA (75).**

*The Case for Atorvastatin as the Study Drug, at Doses Effecting ROCK Inhibition in Humans.* A Phase I safety trial with simvastatin at dose up to 40 mg/day (trials.gov# NCT0176445) noted no deleterious effects in open label enrollment. At least one patient in that trial manifested a dramatic decrease in lesional and brain permeability upon initiating statin therapy (See letter by [name]). That trial was limited to familial cases with common Hispanic *CCM1* mutation, and enrolled cases with largely stable CAs without recent SH. It was not designed to **explore higher statin doses effecting maximal ROCK inhibition**, nor was it designed to include **sporadic and familial cases after recent SH**. While that trial was underpowered, and a different case selection and enhanced biomarkers may have offered better sensitivity, the results argue for dose escalation or for testing another statin. Simvastatin limits dose escalation above 40 mg/day per current USFDA label. Atorvastatin is approved for higher doses, twice as potent as simvastatin in measurable effects (52). **Doses of atorvastatin of 40-80 mg/day are needed to achieve a robust pleiotropic ROCK inhibition effect, specifically assayed in human peripheral blood leukocytes (53, 54).** Rosuvastatin, which allows even higher dose escalation than atorvastatin has not been used as long or by as many patients as atorvastatin. **A systematic review of atorvastatin tolerance and side effects at those doses was carefully considered in the design and safety monitoring plan of the proposed trial.**

*Equivalency of Mouse Versus Human Atorvastatin Dose.* In humans the dosage of statins varies between approximately 0.1–1 mg/kg bodyweight, while most studies in rodents have used doses of 1–100 or even 500 mg/kg (76). An atorvastatin mouse dose of 80 mg/kg/day is equivalent to a calculated “human starting dose” of 44.8 mg/day according to USFDA guidelines: *Human starting dose = Mouse dose X 0.08 (Scaling factor) X 70 kg (Adult weight) (77, 78).* A plasma area under curve (0-24 hours) profile for atorvastatin indicates that a human dose of 96 mg/day replicates the mouse dose of 80 mg/kg/day (79). And per empiric evidence, at least 100 mg/kg/day dose is needed to decrease disease activity in a collagen induced arthritis murine model (80, 81) while atorvastatin at 40 mg/day decreases the disease activity score (DAS28) in arthritis patients (82, 83). And we noted ROCK inhibition effect in mice with atorvastatin 80 mg/kg/day, an effect observed in humans at 40-80 mg/day. Hence **the atorvastatin dose of 80 mg/kg/day in our preclinical experiments corresponds to a human dose range of 40-80 mg/day, commonly used in clinical practice and shown to achieve ROCK inhibition pleiotropic effect.** We propose to use these same doses in the proof of concept trial.

## 3 STUDY DESIGN

### 3.1 Patient Population

The study will enroll 80 adult patients 18-80 years of age (inclusive) with untreated CAs of all genotypes who suffered an adjudicated symptomatic lesional hemorrhage (20) within one year of enrollment. The hemorrhagic lesion would need to have been considered for surgery, and ultimately not resected. We are hence specifically targeting deep and brainstem lesions with greatest risk of rebleeding in the subsequent 2 years, most likely to benefit from stabilizing vascular leak. Given identical somatic mutations and demonstrated lesional ROCK activity (38, 42), cases with sporadic and familial CAs of all genotypes are included (except for post-irradiation cases). Inclusion and exclusion criteria are detailed in Protocol Section 4, aiming to exclude cases receiving prior statin therapy in any form or for any indication in the prior year, cases at high risk for statin intolerance, cases where the hemorrhagic lesion has been treated with surgery or radiation, and other customary exclusions in similar trials. Children will not be enrolled, per Investigational New Drug (IND) exemption restriction for this trial.

The Neurovascular Surgery Program at the U Chicago has an international reputation in CA clinical care and research ([www.uchospitals.edu/ccm](http://www.uchospitals.edu/ccm)) and is the first recognized **Center of Excellence** by the Angioma Alliance ([www.angioma.org](http://www.angioma.org)). During the past 2 years (June 2015 - May 2017) the study PI's clinic evaluated 171 CA patients, and 149 cases, or **87% were enrolled in IRB approved clinical surveillance and biomarker validation projects**. Of these, 37 had suffered a SH during the prior year, 3 of whom were on statin therapy and 7 underwent surgery for lesion excision upon SH (including a case on statin). Hence, 28 subjects (14/ year) would have met inclusion criteria, and at least **12 cases/ year would be enrolled in At CASH EPOC trial from current U Chicago** case activity, based on our 87% enrollment record in IRB studies even without promised intervention. This in addition to cases ("on the docket") who bled in the year prior to trial launch.

We plan to boost trial enrollment from **Chicago Consortium** sites (see letters from NU, Rush UIC Neurosurgery Chiefs, and Chicago StrokeNet PI [name]) targeting >30 CA cases/year with SH for screening, but need only enroll **10 additional cases/year through these regional referrals** and other healthcare professionals in the Chicago Neurological Society (including all practicing neurosurgeons and neurologists serving a 9 million regional population within driving distance of our center). The **Angioma Alliance** (see letter) has identified 48 CA cases throughout the U.S. with SH in the prior year, not taking statins, whose lesion was not resected and who expressed willingness to travel for a trial. We target screening of 20 such cases but need only enroll **5 additional cases/year through this national referral** to meet our enrollment target.

Our team has used similar Chicago consortia to recruit cases for the CLEAR and MISTIE trials. The Angioma Alliance has had a strong record of referring patients from outside Chicago and their enrollment in research studies at our site. We plan a **city wide**

**seminar upon approval of the trial**, and secured its funding from the Kluver Memorial fund at U Chicago, to present it to regional clinicians. **Trial brochure (attached) and trial status updates** shall be e-mailed to members of the Chicago Neurological Society, to the Society of Neurological Surgeons (including all U.S. neurosurgery academic chairs and program directors) and to all registered CA patients in the Angioma Alliance every 6 months. **We intend to facilitate the enrollment and retention** of trial subjects from outside the region, with stipends covering travel expenses for enrollment and follow-up visits. **We note that there is no other ongoing clinical trial of a competing therapy.**

Back up no-cost plan of **extending enrollments into year 4** can be considered, and a last resort option of enlisting another site with accredited biomarker validations, and a record of case enrollment through the **CASH Trial Readiness network** (U01 NS104157, 2017-2022) also led by the trial PI. **Retention is promoted** through scheduled calls every 3 months, and emails with trial status updates every 6 months to enrolled subjects.

### **3.2 Blinding**

The study is designed as a double-blind, placebo-controlled clinical trial. Enrolled subjects will be blinded to treatment rendered, as will the PIs, outcomes assessors processing the radiological biomarkers, the trial staff at the Chicago site and the Data Coordinating Center (DCC) staff at the Baltimore site. Atorvastatin and placebo capsules will be formulated by a third party pharmacy representing two different doses of atorvastatin (40 and 80mg) or placebo. The Research Pharmacy at the Chicago site shall be informed electronically about the treatment allocation (see Section 3.3 Randomization), and it shall dispense the appropriate drug or placebo in a 6-month supply, given at enrollment then mailed by the study team biannually, one month ahead of expected date of exhausting the supply. Subjects in the treatment group will receive unlabeled color coded capsules containing pulverized atorvastatin tablets in the designated doses. Subjects in the control group will receive identical looking color coded capsules containing inactive filler. In the case of dose de-escalation, the Research Pharmacy shall be instructed about the decision to lower the dose, and it shall dispense capsules of different color indicating the lower dose, or identical colored placebo capsules, without breaking the blind to the patient or research team.

The Baltimore statistician shall prepare safety reports including comparison of adverse events (AEs) and interim outcome measures by treatment group labeled as A or B without identifying either as active treatment (See Sections 9.4 on Data Monitoring and 10.3 on Quality Assurance and Data and Safety Monitoring). If a concern is raised about safety and the need to suspend trial enrollment, the independent medical safety monitor (IMSM) may request to identify A or B groups as treatment or placebo. Individual subjects will not be identifiable in the safety reports, maintaining the double-blinding if the trial is resumed.

### 3.3 Randomization

Once a patient is determined to be potentially eligible for participation in the study, the site coordinator or a designated member of the study team at the Chicago site will enter the Inclusion/Exclusion information about the study subject into the VISION (Prelude Dynamics, Austin, Texas) web-based electronic case report form (eCRF) system. The VISION system will process these subject variables, determine eligibility and, if eligible, assign an identification number and treatment method to the patient. The randomization process is handled by an embedded software module designed using SAS (v.9.4 or higher). This module is part of the system and is invoked by the coordinator or investigator within the eCRF system. Randomization is triggered by the investigator or coordinator, via completion of a form in the eCRF, after all eligibility checks are performed. If the coordinator/investigator checks the randomize box and saves the form, the system will automatically set the enrollment date, assign a study ID and trigger the embedded randomization algorithm to determine the randomized treatment (including a final check to make sure the subject meets all eligibility criteria). The site coordinator is provided with a unique, blinded electronic treatment assignment number (randomized patient number) at the end of this process.

***Enrolled subjects are randomized to the atorvastatin or placebo arm in a 1:1 ratio. Randomization shall be stratified by sex, with separate permuted blocks for each sex.*** A unique treatment assignment number (randomized subject number) and its corresponding treatment group allocation will be generated. This shall be communicated electronically through to the Research Pharmacy in Chicago, to appropriately dispense the capsules containing active drug or placebo.

### 3.4 Method of Dosing

After randomization, enrolled subjects in both groups will be given unlabeled color-coded capsules to be taken once daily. In the absence of signs or symptoms of statin-related adverse events (Table 2), subjects will be instructed to continue on the same regimen. The dose may be de-escalated based on subject's tolerance. Subjects reporting adverse events per pre-specified criteria (Category B detailed below) will be put onto the lower dose (40 mg/day) of atorvastatin, with a different color. Subjects randomized to the placebo arm will receive an equivalent supply of identical color unlabeled capsules, devoid of the active ingredient, to be administered in the same fashion as the active drug. They will undergo the same evaluations, dose adjustments, and follow up visits as the treatment cohort.

## 4. SELECTION AND ENROLLMENT OF SUBJECTS

### 4.1 Inclusion Criteria

4.1.1 Age 18-80 (inclusive).

- 4.1.2** Asymptomatic, mild or moderate disability requiring some help but able to attend own bodily needs without assistance. Defined as modified Rankin score (mRS) 0 – 3.
- 4.1.3** Diagnosis of CCM of any genotype supported by relevant imaging studies, where surgical resection is not performed after due consideration per current standard of care..
- 4.1.4** Symptomatic CCM bleeding event within 1 year prior to enrollment.
- 4.1.5** Must be willing/able to travel to the study site for study visits (baseline, 12 and 24 months) over the course of the study.

## **4.2 Exclusion Criteria**

- 4.2.1** Pre-menopausal women who are breastfeeding, pregnant or likely to get pregnant during the study period.
- 4.2.2** Prior surgical treatment of the hemorrhagic CCM lesion.
- 4.2.3** Failure to pass MRI safety screening (claustrophobic, metal implant, etc.).
- 4.2.4** Known allergy or intolerance to gadolinium.
- 4.2.5** Severely impaired renal function (eGFR < 60ml/min), active renal disease or status post-kidney transplants.
- 4.2.6** Statin therapy, for any indication, for more than 7 continuous days or greater than 14 total days within 12 months preceding enrollment.
- 4.2.7** Indication to use statin medication for current approved indication, unrelated to CCM.
- 4.2.8** Known allergy or intolerance to statins.
- 4.2.9** Liver dysfunction or active liver disease (including chronic viral hepatitis) defined as baseline serum transaminases levels twice the upper range of normal.
- 4.2.10** Previous diagnosis of skeletal muscle disorders of any cause (myopathy), or baseline creatine kinase levels five times the upper range of normal.
- 4.2.11** Currently treated with or likely to need treatment with one or more of prohibited medications listed in section 5.3.
- 4.2.12** Active drug or alcohol use or dependence that, in the opinion of the site investigator, would interfere with adherence to study requirements.
- 4.2.13** Serious illness (requiring systemic treatment and/or hospitalization) until subject either completes therapy or is clinically stable on therapy, in the opinion of the site investigator, for at least 30 days prior to study entry.
- 4.2.14** Any other condition that the investigator believes would pose a significant hazard to the subject if the investigational therapy were initiated, including conditions resulting in or precipitating myopathy (e.g. HIV, uncontrolled hypothyroidism).

- 4.2.15** In the investigator's opinion, the patient is unstable, and would benefit from a specific intervention rather than treatment with atorvastatin.
- 4.2.16** Inability or unwillingness of subject or legal guardian/representative to give written informed consent.
- 4.2.17** No documentation of valid healthcare insurance.
- 4.2.18** No medical record confirmation of a primary care physician or other provider of ongoing medical care.
- 4.2.19** Previous cranial irradiation or radiosurgical treatment.
- 4.2.20** Use of ritonavir as an oral drug for COVID-19

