### 5.3.3 Precautionary Interventions

The following drugs interact with Atorvastatin. If unavoidable, extra measures should be put in place for closer monitoring.

- OCP
- Antacids
- Digoxin
- Lipid lowering resins
- Rifampicin
- Grapefruit juice
- Calcium channel blockers

 Values for norethindrone and ethinyl estradiol may be increased, co-administration of statins and an oral contraceptive increased serum levels for norethindrone and ethinyl estradiol. These increases should be considered when selecting an oral contraceptive for a woman taking atorvastatin.

Interfere with absorption of atorvastatin from GI tract

When multiple doses of atorvastatin and digoxin were co-administered, steady state plasma digoxin concentrations increased by approximately 20%. Patients taking digoxin should be monitored appropriately.

As well as other known activators of the Cyt-P450(3A4) isoform which metabolizes most statins in the liver. Interaction affects the pharmacokinetic properties of the drug leading to changes in serum concentration.

Contains one or more components that inhibit Cyt-P450(3a4) and can increase plasma concentrations of atorvastatin, especially with excessive grapefruit juice consumption (>1.2 liters per day).

Weak inhibitors of Cyt-p(3a4) system

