### 5.4 Adherence Assessments

The team is in the process of evaluating potential electronic monitoring devices, an eDiary and a smart bottle. Both devices are equipped with a SIM card and programmed to wirelessly transmit compliance data to the study database in real time. Both devices are linked to a closed loop electronic feedback system that is programmed to set off reminders in escalating manner and ultimately notify the study team. In addition to compliance, these innovative monitoring systems will also allow subjects to notify the team early on of any adverse events or change in concomitant medications. All compliance data will be continuously recorded in the study database and will be used to guide decision-making. In addition, members of the research team in liaison with the local pharmacy will perform pill counts to confirm adherence at the time of follow up visits.

In addition, the TN or research coordinagtor shall contact each subject for scheduled phone calls every three months (to be completed every 10-14 weeks), with a structured questionnaire about compliance and tolerance.

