### **6.2.3 Three month phone call and safety labs (V2)**

The 3 month visit (V2) will consist of a phone call from the Trial Nurse or coordinator as well as laboratory tests. During the phone call, the TN or coordinator will collect information about the patient's current mRS, concomitant medications, and any adverse events. The following laboratory tests need to be completed as part of standard care at 3 months:

- Renal function
- LFT
- CK

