### **6.3.8 Pregnancy**

Because of the unknown teratogenicity profile of the study drug, women of childbearing age are excluded from the trial unless they are surgically sterilized or using a reliable method of contraception. In addition to formal laboratory testing at screening, negative pregnancy status will be confirmed for all women of childbearing potential prior to each MRI evaluation per local institutional policy. Pregnancy during the trial will be considered a safety endpoint; drug administration shall cease but patient will be followed for the duration of the study.

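### Criterion 4.2.1 is looser than the contraception rule in 6.3.8, and month 12 is the only scheduled pregnancy confirmation during dosing that can still stop drug

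*Combined protocol and SAP*

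**What the plan says.** **Eligibility.** Section 4.2, criterion 4.2.1, excludes "Pre-menopausal women who are breastfeeding, pregnant or likely to get pregnant during the study period". It does not mention sterilization or contraception and does not refer to 6.3.8. Section 6.3.8 gives the stricter rule, that "women of childbearing age are excluded from the trial unless they are surgically sterilized or using a reliable method of contraception", and bases it on the drug's unknown teratogenicity. Section 3.1 sends the reader to Section 4 for the inclusion and exclusion criteria. Section 3.3 has staff enter that information in the electronic system: "The VISION system will process these subject variables, determine eligibility and, if eligible, assign an identification number and treatment method to the patient".

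**Follow-up.** Besides the laboratory test at screening, 6.3.8 states that "negative pregnancy status will be confirmed for all women of childbearing potential prior to each MRI evaluation per local institutional policy". Section 6.3.5 places the MRIs at baseline, 12 and 24 months, and Section 5.1 sets 24 months of dosing. On the consequence, 6.3.8 says: "Pregnancy during the trial will be considered a safety endpoint; drug administration shall cease". Section 8 also lists pregnancy as a reason to discontinue.

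**Between MRIs.** Section 5.4 provides "scheduled phone calls every three months (to be completed every 10-14 weeks), with a structured questionnaire about compliance and tolerance". At month 3, "the TN or coordinator will collect information about the patient's current mRS, concomitant medications, and any adverse events" (6.2.3). Sections 6.2.4 and 6.2.6 list the same three items for months 6, 9, 15, 18 and 21. Table 1 marks an assessment of whether to continue the intervention at each of these calls, without describing its content. Contraception during follow-up appears only in the interaction note on oral contraceptives in 5.3.3: "These increases should be considered when selecting an oral contraceptive for a woman taking atorvastatin".

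**The concern.** There are two gaps, both concerning exposure of a pregnancy to study drug.

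First, staff are directed to Section 4 for eligibility, while the objective condition (sterilized, or on reliable contraception) stands in a later section on evaluations. Criterion 4.2.1 asks for a judgment about likelihood and gives no test for it. Someone working from the list alone could admit a woman whom 6.3.8 would exclude. Neither text says that contraception must continue until the last dose.

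Second, the rule that drug stops on pregnancy protects only once the pregnancy is known. If the one scheduled confirmation during dosing is at month 12, a pregnancy between MRIs comes to light only if the participant reports it or general review picks it up. The calls that could ask directly already take place every three months.

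**Working it through.** The plan states no figure on this point. The check compares the two texts and then counts scheduled contacts.

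**Step 1: the two eligibility texts, by type of participant**

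| Woman of childbearing age | 4.2.1 | 6.3.8 |
|---|---|---|
| Surgically sterilized | admitted | admitted |
| Not sterilized, reliable contraception, no plan to conceive | admitted | admitted |
| Not sterilized, no contraception, judged likely to conceive | excluded | excluded |
| Not sterilized, no contraception, judged unlikely to conceive | **admitted** | **excluded** |
| Reliable contraception now, but plans to conceive during the study | excluded | not addressed |

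The fourth row is where 4.2.1 is looser. The documents give no count for it, and it is likely to be small. The fifth row shows that 4.2.1 does look forward over the study period, which 6.3.8 does not. A combined criterion should keep both features.

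**Step 2: scheduled confirmations during dosing**

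Inputs: MRIs at months 0, 12 and 24 (6.3.5); confirmation before each MRI (6.3.8); dosing from month 0 to month 24 (5.1).

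- Month 0 precedes the first dose.
- Month 12 falls within dosing.
- Month 24 is the end of dosing. The visit window of 4 weeks either side (6.2.7) could place it just before the last dose, but it then saves very little exposure.

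Confirmations with 0 < month < 24: month 12 only, so one. Nominal intervals: 12 − 0 = 12 months and 24 − 12 = 12 months.

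**Step 3: what is specified between MRIs**

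| Contact | Specified content | Named pregnancy or contraception item |
|---|---|---|
| Call, month 3 | mRS, medications, adverse events; renal, liver and CK tests; suitability review (6.3.4) | none |
| Calls, months 6 and 9 | mRS, medications, adverse events | none |
| Calls, months 15, 18 and 21 | mRS, medications, adverse events | none |
| Weekly electronic messages | adverse-event questions (10.4.2.6) | none among the six examples given |

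Medication review could show that an oral contraceptive was stopped. It would not show a lapse in a non-drug method.

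**Step 4: effect of one question at the existing calls**

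Pregnancy-specific contacts would fall at months 0, 3, 6, 9, 12, 15, 18, 21 and 24. Each successive difference is 3 months, so the longest nominal interval falls from 12 to 3 months. Calls are completed every 10 to 14 weeks, and 14 weeks is 14 × 7 = 98 days, a little over 3 months. The added contacts are self-report and are not equivalent to the confirmation at month 12.

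**The case against.** The strongest reply is that 6.3.8 already binds the trial and gives content to the looser phrase in 4.2.1, so only a cross-reference is missing. Much of this stands: a reader might infer that the two sections contradict each other, but the documents show an omission and a looser wording. The wording used in the electronic eligibility form is not shown, so it cannot be said that the form applies the weaker text. Consent pages were removed before review, so any contraception instructions there cannot be counted as absent.

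A reader might also infer that the calls contain no question about pregnancy. The documents do not support that. The structured call questionnaire is not reproduced, the questions in 10.4.2.6 are offered as examples, and the manual of operations mentioned in 10.3.2 is not supplied. Because pregnancy is a discontinuation criterion in Section 8, the continuation assessment marked at each call could cover it. Participants must also report new symptoms (Section 7), can reach the trial nurse at any hour (7.1), and are reminded of statin contraindications at months 3 and 12 (6.3.4). What stands is narrower: the protocol specifies no such item for the calls, and defines a suitability review only at screening, 3 and 12 months.

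Finally, a reader might see an error in Table 1, which marks the pregnancy test at screening only. Section 6.3.8 separates the formal laboratory test at screening, which Table 1 marks correctly, from the confirmation before each MRI under local policy. Section 6.3.6 defers to Table 1. No mismatch is shown, and Table 1 needs no change on this account.

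**Conclusion.** The point holds as a minor matter of participant safety. Criterion 4.2.1 lacks the sterilization-or-contraception condition of 6.3.8, for a probably small and uncounted group. Month 12 is the only scheduled confirmation of negative pregnancy status within 24 months of dosing that can still stop drug, and no pregnancy or contraception item is specified for the six quarterly calls. Detection between MRIs is partial and indirect, not absent.

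The size is stated only as a nominal interval between pregnancy-specific contacts: 12 months now, about 3 months with the added question. This assumes the nominal visit schedule and that the unseen call questionnaire has no such item; if it has one, the second change is already in place and needs only to be written into the protocol. The interval is not an estimate of pregnancies or of exposure, for which the documents give no rate. Sample size, power, blinding and the primary analysis are not affected.

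**What to change.** 1. Reword 4.2.1 along these lines: *Women who are pregnant or breastfeeding; and women of childbearing age who are neither surgically sterilized nor using, and willing to continue until the last dose of study drug, a reliable method of contraception.* Cross-refer 4.2.1 and 6.3.8, and confirm that the electronic eligibility form carries the same text.

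2. At the calls at months 3, 6, 9, 15, 18 and 21, as part of the continuation assessment already marked in Table 1, ask non-sterilized women of childbearing age: *Are you, or might you be, pregnant, or have you stopped or changed contraception since the last contact?* If so, hold study drug and obtain a pregnancy test. Apply this alike in both arms.

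The cost is one reworded criterion, one extra question per call for the women concerned, and an occasional triggered test with a short hold on drug. No visit and no routine test is added.
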